## PROTOCOL SUMMARY

Title:	Simulated In-Lab Usability Assessing the Use of Bleep DreamPort-Eclipse
Design:	The study is designed to assess the usability of a novel CPAP human interface compared to a traditional nasal mask.
Objectives:	The objective of this study is to demonstrate the usability of a novel CPAP human interface compared to a traditional nasal mask in a stimulated in-lab setting.
Procedures:	Human subjects will interact with two different CPAP interfaces including a traditional CPAP mask and the 2nd generation DreamPort-Eclipse. Subjects will be requested to put on each of the different CPAP interface options a total of three times for a total of 6 trials. The order of device will be randomized.
Devices:	This comparative study design and data collection will involve the aforementioned two different CPAP interfaces: a traditional CPAP mask and the 2nd generation DreamPort-Eclipse.
Study Sites:	Three investigational sites of Sleep Centers of Middle Tennessee, Advanced Respiratory & Sleep Medicine, and Aeroflow Sleep will participate in the study.
Enrollment:	We plan to recruit 30 participants over the age of 18. We will oversample for participants who are Hispanic or African American. We will aim to recruit participants with the following racial and ethnic breakdown: 30% White; 40% Black; 10% Asian; and 20% Hispanic. We will also recruit an estimated 60% men and 40% women to reflect the OSA population, which affects more men than women.
Eligibility Criteria:	
The subject's eligibility for study enrollment will be reviewed and documented on the appropriate survey form.
 
Inclusion Criteria
 
The subject is a male or female <math>\geq 18</math> years old who are impacted by obstructive sleep apnea and currently are familiar with a CPAP device.
 
Exclusion Criteria
 
Subjects will be excluded if they have any medical or behavioral conditions that would compromise subject safety. Subjects under the age of 18 will be excluded from this study, as the target for this current version of the platform is the adult population.

Primary Endpoint:	
Primary Effectiveness Endpoint:
 
Several metrics will be recorded as part of the usability assessment. Dependent variables will include time to complete each setup, number of technical issues that occurred during the trial, and number of times subjects needed additional instructions. Subjects will also complete a survey at the end of the protocol to evaluate their experience with the different options.

Secondary Endpoints:	NA
Sample Size Estimation:	The purpose of this study is to get feedback on the usability of the device prior to clinical trials. The sample size is based on similar usability studies.
Data Collection:	
All data will be acquired from the research procedures performed during usability assessments on human individuals. Data that will be collected from subjects includes demographic data and survey feedback. All subjects will be represented by subject IDs in the data in order to de-identify data. The individuals that will have the ability to access the subject IDs includes only the principal investigator and sleep center sites.
 
The study will be conducted in accordance with applicable local regulations and national privacy laws. The clinical study will not commence at an investigational site until favorable opinion(s) from the respective Ethics Committee (EC)/ Institutional Review Board (IRB) has been received.

## **Investigator's Responsibility**

Prior to participation in this study, the Investigator must obtain written approval from his/her Institutional Review Board (IRB). This approval must be in the Investigator's name and a copy sent to Bleep ("Sponsor") along with the IRB approved Informed Consent Form (ICF) (if applicable) prior to the start of the study. The Investigator is responsible for training all clinical staff to ensure adequate training is obtained prior to performing any data collection or study-related procedures.

The Investigator must also:

- Conduct the study in accordance with the study protocol, any modifications as requested by the IRB,
- the Declaration of Helsinki, applicable national privacy laws (e.g., Health Insurance Portability and Accountability Act (HIPAA) requirements in the U.S.), applicable Food and Drug Administration (FDA) regulations (e.g., 21 Code of Federal Regulations (CFR) Parts 50, 54, 56, and ISO 14155:2011).
- Ensure that the study does not commence until IRB approval has been obtained.
- If applicable, ensure that written informed consent is obtained from each subject prior to the conduct of any study procedure, using the current IRB-approved ICF.
- Provide all required data and reports and agree to source document verification of study data with subject's medical records.
- Allow Sponsor personnel or their designee(s), as well as regulatory agency representatives and other applicable authorities, to inspect and copy any documents pertaining to the study.
- Provide appropriate resources to ensure compliance with all study-related procedures and prompt submission of all surveys.

The Investigator retains overall responsibility for IRB approval and proper conduct of the study, including obtaining and documenting the Informed Consent process (if applicable), compliance with the study protocol, the collection of all required data, and ensuring that all study personnel have been properly trained on the protocol and have received other necessary training.

## **1. INTRODUCTION**

### **1.1 Introduction**

This Simulated In-Lab Usability Study is a multi-center study to demonstrate the usability of a novel CPAP human interface compared to a traditional nasal mask.

### **1.2 Device Description**

Human subjects will interact with two different CPAP interfaces including a traditional CPAP mask and the next generation DreamPort-Eclipse.

## **2. STUDY OBJECTIVE**

This minimal risk study is being conducted to collect data to compare the usability of three different CPAP modalities. Dependent variables will include time to complete each setup, number of technical issues that occurred during the trial, and number of times subjects needed additional instructions. Subjects will also complete a survey at the end of the protocol to evaluate their experience with the different options.

## **3. STUDY DESIGN**

This multicenter study will involve recruiting 30 adult subjects who are impacted by obstructive sleep apnea and currently are familiar with a CPAP device. Clinicians will screen subjects for cognitive deficits and serious mental health or medical conditions that would compromise subject safety or accurate user feedback. Prior to data collection and study enrollment, the protocol will be explained in detail to the subjects and informed consent will be obtained.

Participants will receive and review the training materials developed in Aim 1, including written and video instructions on how to use the DreamPort-Eclipse. They will also be provided with and review instructions on the traditional nasal mask used in this study. Participants will be requested to put on each of the different CPAP interface options a total of three times for a total of six trials. The order of device trials will be randomized.

## **4. STUDY ENDPOINTS**

### **4.1 Primary Effectiveness:**

The primary endpoints for this study will include time to complete each setup, number of technical issues that occurred during the trial, and number of times subjects needed additional instructions. Subjects will also complete a survey at the end of the protocol to evaluate their experience with the different options.

## **4.2 Secondary Endpoints:**

None.

## **5. STUDY POPULATION**

### **5.1 Number of Subjects**

Data collection will continue until **30** eligible subjects have been enrolled across our three study locations.

### **5.2 Eligibility Criteria**

Subjects will be enrolled into the study based upon the inclusion/exclusion criteria listed below.

#### **5.2.1 *Inclusion Criteria***

To be eligible for inclusion in this study, a subject must meet the following criteria:

The subject is a male or female  $\geq 18$  years old who is impacted by obstructive sleep apnea and currently is familiar with a CPAP device.

#### **5.2.2 *Exclusion Criteria***

Subjects will be excluded if they have any medical or behavioral conditions that would compromise subject safety. Subjects under the age of 18 will be excluded from this study, as the target for this current version of the platform is the adult population.

## **6. INDEX PROCEDURE, EVALUATIONS, AND SCHEDULE**

### **6.1 Enrollment**

#### **6.1.1 *Informed Consent and Enrollment***

Prior to data collection and study enrollment, the protocol will be explained in detail to the participants and informed consent will be obtained. All participants will provide written informed consent prior to participation. The information about the research will be provided to the participant in written form as well as read aloud to the participant.

Prior to the collection of any study-specific data or conduct of any study-specific procedures, the subject must voluntarily provide written informed consent (if needed) and comply with

This document contains information that is the confidential and proprietary property of Bleep or its affiliates. Neither this document nor the information therein may be reproduced, used, or disclosed to or for the benefit of any third party without the prior consent of Bleep.

applicable national privacy laws. All study procedures will be documented in the medical record and/or source document and on study case report forms (CRFs).

#### **6.1.2 *Demographics and Medical History***

The subject's demographic information will be collected and documented on the appropriate CRFs (i.e., Age (years), sex and initials).

#### **6.1.3 *Physical Examinations***

No physical examination will take place.

#### **6.1.4 *Assignment of Subject Number***

A unique participant identification number (PID) will be assigned to enrolled subjects. Participant or Subject numbers will be assigned in sequential order. The Participant or Subject number will consist of six digits. The first three digits will designate the study site. The last three digits will designate the subject by number in sequential order (e.g., 210-001, 210-002...).

### **6.2 *Index Procedure Data***

#### **6.2.1 *Index Procedure Details***

Index procedure details will be collected on all enrolled subjects. The Index procedure is defined as the SNAP CPAP usability protocol in accordance with the instructions for use (IFU). Such details related to this protocol may include, but are not limited to the following:

- Date of Usability Test
- Product Name, Catalogue Number, Lot Number
- Configuration Details
- Indication
- Accessory details
- All adverse events, device malfunction, and complications related to device or procedure

### **6.3 *Clinical Follow-Up***

There is no clinical follow-up associated with this study.

## **7. ASSESSMENT OF SAFETY**

This document contains information that is the confidential and proprietary property of Bleep or its affiliates. Neither this document nor the information therein may be reproduced, used, or disclosed to or for the benefit of any third party without the prior consent of Bleep.

The Investigator is responsible for the detection and documentation of events meeting the criteria and definition of an Adverse Event (AE), Serious Adverse Event (SAE) and unanticipated Adverse Device Effects (UADE) as provided in this protocol. The occurrence of AEs should be documented in the source documents and reported using the appropriate CRF. Events that occur prior to the index-procedure should be captured within the subject's medical history.

## 7.1 Definition of Events

### 7.1.1 *Adverse Events (AE)*

An AE is defined as any untoward medical occurrence, unintended disease or injury, or untoward clinical signs (including abnormal laboratory findings) in subjects, users or other persons, whether or not related to the study device [ISO14155:2011 (E)].

Abnormal laboratory results are not to be considered AEs unless the results are accompanied by clinical signs or symptoms. Preexisting conditions should be considered as part of the subject's medical history. Any medical condition that is present before the implantation procedure will be considered medical history and should not be reported as an AE. However, if the subject's condition deteriorates, or there is a substantial increase in severity or frequency of the condition (worsening of the underlying disease), which has not been attributed to natural history during the subject's clinical follow-up, it will be recorded as an AE.

### 7.1.2 *Serious Adverse Event (SAE)*

Each AE will be assessed to determine whether it is serious or non-serious. (Note: the term serious is not synonymous with severity, which may be used to describe the intensity of an event experienced by the subject). A SAE is an AE that:

1. Led to death; or
2. Led to serious deterioration in the health of the subject, that either resulted in:
  - a. A life-threatening illness or injury;
  - b. A permanent impairment of a body structure or body function;
  - c. In-patient or prolonged existing hospitalization (>24 hours); or
  - d. Medical or surgical intervention to prevent life-threatening illness or injury or permanent impairment to a body structure or body function
  - e. Led to fetal distress, fetal death, or a congenital abnormality or birth defect.

NOTE: Planned hospitalizations for a preexisting condition (prior to device use), or a procedure without serious deterioration in health, are not considered an SAE.

## 7.2 Severity of Adverse Events

This document contains information that is the confidential and proprietary property of Bleep or its affiliates. Neither this document nor the information therein may be reproduced, used, or disclosed to or for the benefit of any third party without the prior consent of Bleep.

Each AE should be assessed for its severity, or the intensity of an event, experienced by the subject.

1. **Mild:** Awareness of a sign or symptom that does not interfere with the subject's activity or is transient and is resolved without treatment or sequelae.
2. **Moderate:** May interfere with the subject's activity and require additional intervention and/or treatment and may have additional sequelae.
3. **Severe:** Significant discomfort to the subject and/or interferes with their activity. Additional intervention and/or treatment are necessary. Additional sequelae occur. Severe is used to describe the intensity of an event experienced by the subject.

### 7.3 Relationship of Adverse Event to Device/Procedure

Each AE/SAE will be assessed for its relationship to the product(s) being studied or surgical procedures as follows:

1. **Device-Related:** This category should be restricted to AEs directly attributable to the devices being studied in the study.

The following categories will be used to assign the certainty of the relationship:

1. **Definitely Related:** An AE is definitely related if the AE is known to occur with the product(s), there is a reasonable possibility that the product(s) caused the AE, or there is a temporal relationship between use of the product(s) and the event. Reasonable possibility means that there is evidence to suggest a causal relationship between the product(s) and the AE.
2. **Possibly Related:** An AE is possibly related if it is capable of being related but relatively unlikely.
2. **Not Related:** An AE is not related if it is determined that there is no reasonable possibility that the product(s) caused the event, there is no temporal relationship between the product(s) and event onset, or an alternate etiology has been established.

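### Section 7.3: Definitely Related and Not Related are each met by a single criterion and overlap with no precedence rule, and Possibly Related cannot stand alone once timing or causal evidence is determined

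*Combined protocol and SAP*

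**What the plan says.** Section 7.3 applies to all events: "Each AE/SAE will be assessed for its relationship to the product(s) being studied". It then introduces three grades with the sentence "The following categories will be used to assign the certainty of the relationship".

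- **Definitely Related.** Three criteria joined by *or*: the event is a recognised effect of the product, "there is a reasonable possibility that the product(s) caused the AE, or there is a temporal relationship" between use and event. The section adds: "Reasonable possibility means that there is evidence to suggest a causal relationship between the product(s) and the AE".
- **Possibly Related.** "An AE is possibly related if it is capable of being related but relatively unlikely". This definition uses none of the criteria that define the other two grades.
- **Not Related.** Three criteria, also joined by *or*: there is no reasonable possibility of causation, "there is no temporal relationship between the product(s) and event onset, or an alternate etiology has been established".

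Just before the grades, the section describes a Device-Related type of event: "This category should be restricted to AEs directly attributable to the devices being studied in the study". Neither section 7.3 nor any other section says which certainty grade takes precedence when an event meets more than one.

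**The concern.** A certainty scale should place each event in one grade. Here the top and bottom grades are each reached by one criterion, and the two lists are not opposites of each other. An event can therefore qualify for both, and the middle grade has little or no territory of its own.

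What is at stake is the consistency of the causality labels. Thirty subjects are to be enrolled at three sites (section 5.1). Two investigators who see similar events could assign opposite grades, and both would be following the protocol. Relatedness also bears on the device- or procedure-related complications collected under section 6.2.1 and on the unanticipated adverse device effects that section 7 makes the investigator responsible for detecting. Section 7.3 is the only text on causality available for either purpose. In a small study with few events, one or two arbitrary labels could change the reported device-related picture.

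**Working it through.** The documents give no figure on this point, so there is none to reproduce. The check is a full enumeration of the definitions.

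**Inputs, all from section 7.3.** K = recognised effect of the product; R = reasonable possibility of causation; T = temporal relationship; E = another cause established.

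- Definitely Related = K or R or T
- Not Related = (not R) or (not T) or E

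**Step 1: count the 16 yes/no combinations.**

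- Definitely Related fails only if K, R and T are all absent: 2 combinations (E yes or no). Both meet Not Related.
- Not Related fails only if R and T are present and E is absent: 2 combinations (K yes or no). Both meet Definitely Related.
- The rest meet both: 16 − 2 − 2 = 12. None meets neither.

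**Step 2: particular cases.**

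- Exactly one of K, R, T present: 3 × 2 = 6 combinations. R and T are never both present, so all 6 also meet Not Related.
- T and E both present (an event during use with another established cause): 4 combinations, and all 4 meet both grades.
- T present: 8 combinations. All 8 meet Definitely Related and 6 of them also meet Not Related.

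**Step 3: what is left for Possibly Related.** If T is present, Definitely Related is met; if T is absent, Not Related is met. The same holds for R. So whenever timing or causal evidence is determined, at least one extreme grade applies.

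**Step 4: sensitivity to how the text is read.**

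| Reading | Combinations | Meet both | Meet neither |
|---|---|---|---|
| As written | 16 | 12 | 0 |
| R may be undetermined | 24 | 16 | 0 |
| Any criterion may be undetermined | 81 | 37 | 4 |
| R assumed to require T present and E absent | 10 | 6 | 0 |
| *And* in place of *or* in one list | 16 | 1 | 1 |
| *And* in place of *or* in both lists | 16 | 0 | 12 |

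The 4 of 81 are the combinations with R and T both undetermined, K not present and E not established: 1 × 1 × 2 × 2 = 4. The 37 follows from 81 − 24 − 24 + 4, where 24 combinations fail each extreme grade (8 × 3) and 4 fail both.

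**Step 5: would a partial repair do?** Suppose only the timing routes are removed and E is made to exclude the top grade: Definitely Related = (K or R) and not E; Not Related = (not R) or E. The 16 combinations then split into 4 Definitely Related only, 10 Not Related only, 2 both (K present, R and E absent) and 0 left for Possibly Related. The routes through R alone and K alone must close as well.

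**The case against.** **Judgement and training.** Investigators will grade by judgement, and section 11.3 requires training on data collection. Both may reduce inconsistency. Neither supplies a rule, and judgement would have to override the stated criteria.

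**The criteria are not independent.** This is correct, and the share of overlapping combinations depends on which are counted as possible. If a reasonable possibility is assumed to need compatible timing and no established other cause, 6 of 10 overlap instead of 12 of 16. The overlap survives, and the single example of an event during use with another established cause is enough to show it.

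**Undetermined inputs.** Not Related speaks of what has been determined, so some inputs may be unknown. A reader might infer that Possibly Related can never be the sole grade. That goes too far: it can stand alone when causal evidence and timing are both undetermined. The exception is narrow, because timing will normally be known in an observed in-lab session with no follow-up (section 6.3).

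**The Device-Related sentence.** Its wording on direct attribution might seem to hold back the top grade. It describes a type of relationship and does not rank the certainty grades. Its tension with a timing-only route is a secondary matter of interpretation.

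**Little depends on the grade.** This stands, and it limits the weight of the point. Section 2 calls the study minimal risk. Sections 4.1 and 4.2 list no safety endpoint, section 8.2 plans no adverse event analysis, and no reporting or stopping rule is tied to the grade. Events are recorded whatever their grade: "The occurrence of AEs should be documented in the source documents and reported using the appropriate CRF".

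**Conclusion.** The definitions are contradictory as written. On the literal *or* wording, with each criterion taken as known, 12 of 16 combinations meet both opposite grades and none meets neither. The middle grade cannot be the only one met once timing or causal evidence is determined.

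Three stronger readings are not supported:

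- The 12 of 16 is not a rate of mislabelled events. The documents give no adverse event rate, and the combinations are not equally likely.
- A reader might infer that the three sites would grade one and the same event differently. Nothing in the documents has several sites grade one event; the risk is inconsistent grading of similar events.
- A reader might treat this as a flaw in the analysis. The effect stops at AE/SAE causality labels and the related complications and unanticipated device effects. The usability endpoints, the ANOVA and the sample size are untouched.

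This is a minor correction to a safety definition, worth making because the grading is mandatory and the repair is wording alone.

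**What to change.** Reword the three definitions in section 7.3, and on the CRF where the grade is recorded, so that each event falls into exactly one grade:

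1. No single criterion (timing alone, a reasonable possibility alone, or being a recognised effect alone) should be enough for Definitely Related.
2. Events with a reasonable possibility of causation that fall short of Definitely Related go to Possibly Related. Reconcile that grade's current description of the relationship as improbable with the section's own meaning of reasonable possibility, which is evidence suggesting causation.
3. State which grade prevails when another cause is established and there is also evidence that the device contributed. This must fit section 7.1.1, which records worsening of a pre-existing condition as an adverse event. A rule sending every event with another established cause to Not Related would include events that the device had aggravated.
4. If the top grade is to rest on stronger causal evidence than the middle one, say how the two levels of evidence differ in practice.

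The exact causality criteria are for the sponsor to choose; the wording can be checked with the same enumeration. The cost is protocol and CRF text, covered in the training already required by section 11.3. Sample size, visits and the usability analysis do not change.
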